Patients will be approached in the office setting after it has been determined that they have failed conservative management of advanced knee arthritis. Patients will be in the surgeons' clinic behind closed doors with the performing surgeon and another member of the research team. Consent will be obtained in the office after scheduling total knee arthroplasty procedure. The consent process is expected to take 30 minutes, but more time is available to ensure that patients have all their questions answered prior to signing the consent form.

Sharing of Results with Research Participants

- Results will not be shared with research participants
- Results will not be shared with research participants' doctors

Study Design

Prospective randomized control cohort study

Study Procedures

Patients will be enrolled in study prior to surgery, outlined above in the consent process.

At the time of patient enrollment, A trained member of the research team will measure the circumference of the patient's leg at the mid-thigh, mid-knee and mid-calf with the leg in full extension. The patient's range of motion of the operative leg will be measured in flexion and extension. The patient will also fill out a baseline Western Ontario and McMaster Universities Osteoarthritis Index (WOMAC) Questionnaire. All measurements and questionnaire answers will be recorded on the study data collection sheet and will be transferred to RedCAP. At this time, patient's will be assigned a unique study identifier which will be randomly assigned to the experimental or control group. Unique study identifier numbers will start at "#1" and will go up by one additional number with every patient enrolled in the study. Even numbers will be assigned to the control group and odd numbers will be assigned to the study group, ending with 50 people enrolled in each group.

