The patient will then go on to have their primary total knee arthroplasty by standard of care procedure. Both cruciate retaining and posterior stabilized total knee replacement designs will be included in the study. Following closure of the surgical site and placement of a postoperative occlusive dressing, the operative leg will be measured once more for circumference and range of motion, and the values will be recorded on the study data collection sheet and transferred into redcap. The patient will then be placed in their randomized post-operative sleeve/device and will be transferred to the PACU and will receive the standard postoperative treatment.

Pre-operative, intra-operative and post-operative pain protocols will be uniform across performing surgeons and will include pre-operative adductor canal block, intra-operative posterior capsular injection of local anesthetic, and a standardized post-operative medication regimen consisting of:

- Percocet 5/325mg every 6 hours #28 pills
- Ibuprofen 800mg every 8 hours x 14 days
- Carisoprodol 250mg every 8 hours x 14 days
- Gabapentin 300mg every evening x 14 days

- Enteric Coated Aspirin 325mg every 12 hours x 28 days (for DVT prophylaxis)
- Ascorbic Acid 500mg every 12 hours x 14 days
- Colace 100mg every 12 hours for 7 days

On post-operative day one, patient's will be seen and evaluated in their inpatient rooms. Their leg measurements will be taken again with the knee sleeve/compressive gradient dressing pulled down. Measurements will be recorded on the data collection sheet and transferred to RedCAP. Patient's skin will be inspected for any reactions to the sleeve and a standard postoperative examination will be performed to ensure no neurovascular compromise, blood clots, infections or other post-operative complications. The number of oral narcotic pain medications consumed since time of surgery will also be recorded on the data collection sheet and transferred into RedCAP.

Patients will likely be discharged on post-operative day 1. Patients that have not been discharged on post-operative day 1 will not be measured on post-operative day 2.

Sleeves will be worn morning and night for 2 weeks, removing them only for hygiene and washing of the sleeve. After 2 weeks, the patient's will wear the sleeve as much as they can tolerate day and night. At 6 weeks, sleeves will be discontinued all together. Final ROM and Circumference Measurements will be obtained at 12 weeks post-operative mark.

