Visual analog Pain scale
Pain medications consumed
Adverse clinical events including DVT, stroke, PE, surgical site infection, reoperation Name
Medical record number
Patient demographics (age, sex, weight, height, BMI)

Data Analysis Plan

Demographics will be reported using descriptives such as count data and percentages. Differences between groups at baseline (pre-op) will be reported using two-tailed independent ttests for continuous variables, and chi-square or Fisher's Exact tests for categorical data, as appropriate.

The primary outcomes of range of motion, leg circumference, and pain ratings will be compared post-op between conditions using two-tailed independent t-tests. Should clinically relevant

demographics differ significantly between conditions pre-op (baseline), post-op comparisons will instead be conducted using one-way ANCOVAs controlling for differences at pre-op (baseline). These comparisons will additionally be made at multiple additional time-points throughout a 12- week post-op time period.

A priori power analyses were calculated for two-tailed independent t-tests for each primary outcome, using an alpha of .05, power = .80. Each of these are reported and the average of these numbers is used to calculate the final sample size. Clinically significant reductions in pain are defined as a 2-point change with a standard deviation of 2.5 using a 10-point scale; 84 patients were estimated. Clinically significant changes in range of motion are defined as: 10 degrees of difference from a 0-140 degree estimated range of values. Clinically significant changes in leg circumference are defined as: 1 cm difference in leg circumference using a 15-30 estimated range of values. To identify medium effect sizes of .55, 106 patients were estimated. Averaging these values, 99 patients were estimated. To ensure equal numbers of patients in each condition, 100 patients will be recruited for this study.

Risks to Research Participants

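### Two hand-measured primary outcomes have no assessor masking: the garment is in view on day 1 and the study number can reveal the arm, so measurement bias is possible and cheap to reduce

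*Combined protocol and SAP*

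**What the plan says.** The Data Analysis Plan names the outcomes and the test: "The primary outcomes of range of motion, leg circumference, and pain ratings will be compared post-op between conditions using two-tailed independent t-tests". It adds comparisons at further time points up to 12 weeks and does not single out one visit as primary.

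Study Procedures and the Study Timeline set the measuring schedule. On the measurer, the garment and the study number they say this:

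- **Enrolment.** "A trained member of the research team will measure the circumference of" the leg at three levels, and range of motion is taken. No other visit has a named measurer.
- **Study number.** Numbers run in order from 1, and "Even numbers will be assigned to the control group and odd numbers will be assigned to the study group".
- **End of surgery.** The leg is measured and the values recorded. Only after that: "The patient will then be placed in their randomized post-operative sleeve/device".
- **Post-operative day 1.** "Their leg measurements will be taken again with the knee sleeve/compressive gradient dressing pulled down". The same visit includes a check of the skin for reactions to the sleeve.
- **Weeks 2, 4 and 6.** Both measurements are scheduled, but the text does not say whether the garment is on, pulled down or off when they are taken. At the last of these visits wear ends: "At 6 weeks, sleeves will be discontinued all together".
- **Week 12.** "Final ROM and Circumference Measurements will be obtained at 12 weeks post-operative mark".

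No section mentions masking of the person who measures. The only hint on staffing is in Consent Process, where the patient is seen "with the performing surgeon and another member of the research team".

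**The concern.** Tape position, tape tension and the judgement of end range all leave room for expectation to influence the reading. The trial asks whether the new garment does better than the standard stocking, so staff may hold such an expectation.

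The target differences are 1 cm for circumference and 10 degrees for range of motion. A difference in measurement error between arms of even part of that size enters the t-test exactly as a treatment effect would. The fallback ANCOVA does not help: it adjusts for differences at baseline, and a lean that arises after allocation is not in the baseline values. Protection has to come from how the measurement is done, and it cannot be added once the data are collected.

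**Working it through.** **1. The plan's own figure.** For range of motion and circumference the plan gives d = 0.55, two-sided alpha 0.05, power 0.80 and 106 patients. By the normal approximation, n per arm = 2 × (1.960 + 0.842)² / 0.55² = 51.9, so 52 per arm and 104 in total. The exact two-sample t-test gives 53 per arm, or 106. The figure reproduces.

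**2. Standard deviations.** The plan states none for these two outcomes, so they are assumed over a range:

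- From the target difference and d = 0.55: 1 / 0.55 = 1.82 cm and 10 / 0.55 = 18.2 degrees.
- From the plan's estimated ranges divided by 6: 15 / 6 = 2.5 cm and 140 / 6 = 23.3 degrees.
- From the same ranges divided by 4: 15 / 4 = 3.75 cm and 140 / 4 = 35 degrees.

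The circumference range carries no unit in the plan and is read here as centimetres.

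**3. Lean.** The plan gives no figure. The values used are half and a quarter of each target difference: 0.5 and 0.25 cm, 5 and 2.5 degrees. Each is taken as a constant shift in favour of the garment.

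**4. Test.** Study Procedures gives 50 per arm, so df = 98 and the critical t is 1.984. With no true effect, the t statistic has noncentrality (lean / SD) × √(50/2) = 5 × lean / SD. The chance of a false benefit is the probability that this noncentral t exceeds 1.984. With zero lean it is 2.5%.

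Worked case: 0.5 / 1.82 = 0.275, noncentrality 5 × 0.275 = 1.375, chance 27.5%.

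| Outcome and lean | Smallest SD | Middle SD | Largest SD |
|---|---|---|---|
| Circumference, 0.5 cm (SD 1.82 / 2.5 / 3.75) | 27.5% | 16.6% | 9.7% |
| Circumference, 0.25 cm | 10.0% | 7.1% | 5.2% |
| Range of motion, 5 degrees (SD 18.2 / 23.3 / 35) | 27.5% | 18.4% | 10.5% |
| Range of motion, 2.5 degrees | 10.0% | 7.6% | 5.4% |

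These are rates per test, in the direction of benefit only.

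**5. Scale check.** The smallest observed difference that reaches significance is 1.984 × √(2/50) = 0.397 SD. At the smallest SDs that is 0.72 cm or 7.2 degrees, so a lean of 0.5 cm or 5 degrees would supply about 69% of it (0.5 / 0.72).

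**6. Which visits are exposed.**

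| Visit | Garment in view? | Could the study number reveal the arm? |
|---|---|---|
| Immediate post-op | No, not yet applied | Yes, if seen and the rule is known |
| Day 1 | Yes, as written | Same |
| Weeks 2 and 4 | Not stated; plausible | Same |
| Week 6 | Not stated; wear ends at this point | Same |
| Week 12 | No, wear stopped six weeks earlier | Same, or through memory of earlier visits |

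**The case against.** The strongest reply is that the documents establish less than a reader might infer.

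- **That the measurer knows the arm throughout.** Garment visibility is written down for day 1 only. The parity rule makes the arm readable, but nothing says that the measurer sees the number, that the measurement sheet carries it, or that the measurer knows the rule. This stands: the measurer can learn the arm, but is not shown to know it.
- **That the results would be biased.** Both the lean and the SD are assumptions, and the calculation supposes that every measurer leans the same way by the same amount. At the largest SD a 0.25 cm lean moves the false-benefit rate only from 2.5% to 5.2%. This stands: the table shows sensitivity and does not estimate the actual bias.
- **That existing staff can mask every measurement.** The documents give no measuring roster for the two sites. If one person measures, inspects the skin and examines the limb on day 1, that person is unmasked for later visits. This stands: feasibility is for the investigators to confirm.
- **That the garment can simply be taken off first.** For the first two weeks Study Procedures allows removal only for hygiene or for washing the sleeve. Full removal for measurement would conflict with that text.
- **That the whole primary analysis is affected.** No primary visit is fixed, so the exposed share is unknown.

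None of this supplies the missing provision. The plan remains silent on masking for two judgement-dependent primary outcomes, and it writes an unmasked procedure into day 1.

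**Conclusion.** The point holds as a gap in protection. Circumference and range of motion have no assessor masking, day 1 is openly unmasked, and the numbering scheme could reveal the arm at any visit after allocation.

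If there were a constant lean of half the target difference and no true effect, the chance of a significant result favouring the garment would be roughly 10% to 28% per test instead of 2.5%. With a quarter of the target difference it would be about 5% to 10%. These figures rest on 50 analysed patients per arm, the assumed SDs and an assumed lean. A lean the other way would hide a real benefit instead.

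The documents do not show that such a lean exists, and they do not say who measures after enrolment. The case for change is that the remedy is inexpensive and the planned analysis offers no substitute for it. Sample size, visits and outcomes are unaffected.

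**What to change.** Amend Study Procedures as follows.

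1. Label measurement sheets with an ID that does not encode the arm, and do not reveal the arm to the measurer until after the immediate post-operative measurement.
2. On day 1, and at any later visit where the garment is worn, have the pulled-down garment covered, for example with a drape, before the measurer approaches. If the investigators prefer full removal, they must first reconcile it with the protocol's wear instruction.
3. Record circumference and range of motion before the skin inspection and before any discussion of the garment.
4. Where existing team members allow, use a measurer who has not been told the arm, including at week 12. The investigators should confirm feasibility at both sites and state in the protocol who measures at each visit.

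The cost is a separate measurement ID with its linking list and a minute or two per visit. Masking will be imperfect, because skin marks or a patient's remark can reveal the arm. These steps do not protect patient-reported pain or WOMAC.

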Patients will be asked to fill out the WOMAC questionnaire at the time of consent, postoperative day 1 and at each subsequent post-operative visit.

Patients will be seen back at regularly scheduled post-operative visits of 2 weeks, 4 weeks, 6 weeks and 12 weeks. Patients will be given a WOMAC questionnaire to fill out at each visit. They will also give a numerical score for their perceived average pain level since their last visit. Patients will also be asked to bring in their narcotic pain pills to the post-operative appointment so they can be counted. The WOMAC questionnaire, leg circumference, knee range of motion, average pain score and number of remaining narcotic pain pills will be collected on the data collection sheet and transferred to RedCAP. Any complications will also be recorded.

The Reparel leg sleeve is the experimental device being investigated in this study. It is intended to improve swelling in the post-operative knee. Further description of the device is provided in the background section of this protocol

EPIC Electronic Medical Records will be used to collect data about patients during their inpatient, post-operative stay. Ambulatory EMR will be used in the outpatient setting to collect data and track post-operative clinic visits.

Study Timeline

	Pre-Screening	Time of Consent	Post-op	Post-op day 1	2 week post-op	4 week post-op	6 week post-op	12 week Post-op
Total Estimated time of visit	30 minutes	35 Minutes	5 minutes	30 minutes	30 minutes	30 minutes	30 minutes	30 minutes
WOMAC Questionnaire		x		x	x	x	x	x
Leg Circumference measurements		x	x	x	x	x	x	x
Knee Range-of-motion		x	x	x	x	x	x	x
Review of pain scale and narcotic use log				x	x	x	x	x

The enrollment period will be 1 year from the time of the first patient enrolled in the study. The enrollment period may be expanded to allow for the investigators to reach their goal of 100 patients. The total amount of time each patient will be involved in the study will be 12 weeks. Patients will only be required to wear the post-operative sleeve/dressing for 6 weeks post-operatively. Patients will continue to report their narcotic consumption and average pain scores for 12 weeks post-operatively.

Data to be Collected for your study (AFTER consent and HIPAA Authorization have been obtained)

Mid-thigh, mid-knee, and mid-calf measurements in extension
Range of motion measurements in knee flexion and knee extension
Western Ontario and McMaster Universities Osteoarthritis Index (WOMAC)

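### Pain is a primary outcome with no pre-operative rating, so its comparison cannot be checked or adjusted at its own baseline; this costs precision, not validity

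*Combined protocol and SAP*

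**What the plan says.** The Data Analysis Plan makes pain a primary outcome and sets the default test: "The primary outcomes of range of motion, leg circumference, and pain ratings will be compared post-op between conditions using two-tailed independent t-tests". The move to ANCOVA is conditional. It applies if clinically relevant "demographics differ significantly between conditions pre-op (baseline), post-op comparisons will instead be conducted using one-way ANCOVAs controlling for differences at pre-op (baseline"). The plan does not say whether the covariate is the demographic that differs or the outcome's own pre-operative value.

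At enrolment, Study Procedures lists leg circumference, range of motion and one questionnaire: "The patient will also fill out a baseline Western Ontario and McMaster Universities Osteoarthritis Index (WOMAC) Questionnaire". It names no pain rating. In the Study Timeline, the row "Review of pain scale and narcotic use log" is blank at consent and immediately after surgery. It is ticked at post-operative day 1 and at weeks 2, 4, 6 and 12. The list of data to be collected includes "Visual analog Pain scale" without a time point.

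For the clinic visits at weeks 2 to 12, Study Procedures describes the rating this way: "They will also give a numerical score for their perceived average pain level since their last visit". No recall period is given for the day-1 rating.

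**The concern.** Range of motion and circumference both have a consent-visit value; pain is the only primary outcome without one. Three things follow.

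- The planned baseline group comparisons have nothing to compare on the pain scale. Allocation by odd and even enrolment number is a separate matter, but it makes a direct look at baseline pain more useful than usual.
- An ANCOVA on baseline pain is unavailable, although it is the ordinary way to gain precision for an outcome of this kind.
- The plan defines the clinically significant effect as a reduction, expressed as a 2-point change, but no patient's change from before surgery can be calculated on this scale.

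A secondary point is that the recall period varies between visits and is undefined on day 1, so the ratings do not measure the same quantity at each time point.

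**Working it through.** **Inputs.** The Data Analysis Plan gives SD 2.5, a 2-point difference, a two-sided t-test and "using an alpha of .05, power = .80". Study Procedures gives 50 patients per arm. I take 2.5 as the within-arm SD of the post-operative rating and assume complete data. The correlation r between a pre-operative rating and the post-operative rating is not in the documents, so I show .2 to .7.

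**The plan's own figure.** The stated total for pain is 84. With d = 2/2.5 = 0.80:

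- Normal approximation: n per arm = 2 × (1.96 + 0.842)² / 0.80² = 24.5, so 25 per arm and 50 in total.
- t-test: 52 in total.

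The stated 84 is not reproduced at power .80. The t-test gives 84 at power .95. The 106 for effect size .55 is reproduced by the t-test, and (84 + 106 + 106)/3 = 98.7 gives the stated 99. The mismatch in the 84 should be reconciled separately; nothing below depends on it.

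**Effect of a baseline covariate.**

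- SE of the difference = 2.5 × √(1 − r²) × √(2/50). At r = 0 this is 2.5 × 0.2 = 0.500.
- 95% half-width = t(.975, 98) × SE. At r = 0 this is 1.984 × 0.500 = 0.99.
- Equivalent unadjusted total N = 100/(1 − r²).
- Difference detectable at 80% power = (1.96 + 0.842) × SE, by normal approximation.

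| Assumed r | SE | 95% half-width | Equivalent N | Detectable difference | Power, 2 points | Power, 1 point |
|---|---|---|---|---|---|---|
| 0 (no baseline) | 0.500 | 0.99 | 100 | 1.40 | 97.9% | 52% |
| .2 | 0.490 | 0.97 | 104 | 1.37 | 98.3% | 53% |
| .3 | 0.477 | 0.95 | 110 | 1.34 | 98.7% | 55% |
| .5 | 0.433 | 0.86 | 133 | 1.21 | 99.6% | 64% |
| .7 | 0.357 | 0.71 | 196 | 1.00 | >99.9% | 80% |

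**Against the WOMAC alternative.** The first row is the right comparator only if no covariate would be used. As an illustration, suppose baseline WOMAC pain correlated .3 with the outcome and a same-scale rating .5. The same-scale rating would then take the half-width from 0.95 to 0.86, a gain of 0.09, instead of 0.99 to 0.86, a gain of 0.13.

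**Recall period.** With visits at weeks 2, 4, 6 and 12, the look-back is about two weeks at each of the first three and six weeks at the last. It is longer for anyone who misses a visit. On day 1 it is unstated, whereas the day-1 narcotic count is explicitly anchored to surgery.

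**The case against.** The strongest reply is that the plan does not need a baseline pain rating. A reader might infer that it calls for a baseline-adjusted pain comparison that cannot be carried out. The documents do not support that. The default is an unadjusted comparison of post-operative values. The ANCOVA is triggered by imbalance in demographics, and age, sex, weight, height and BMI are all collected. On the plainest reading those are the covariates, so the ANCOVA can be run for pain. It fails only if the covariate is read as the outcome's own baseline, which the text leaves open. This part of the reply stands in full.

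A reader might also infer that chance imbalance in pre-operative pain biases the result. It does not: the unadjusted standard error already allows for it. What is lost is precision.

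Baseline WOMAC is a usable proxy, so imbalance can be examined indirectly and some of the precision recovered. That stands, although the plan does not name WOMAC as a covariate and it is not the primary pain scale. Power for 2 points is also already high, and at r = .3 the half-width falls by only about 0.04 points.

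Finally, a reader might take the day-1 rating to reach back to the consent visit and so mix arthritis pain with surgical pain. The recall sentence follows the list of week-2 to week-12 visits, so it does not govern day 1; the day-1 period is simply unstated. The longer window at week 12 applies equally to both arms.

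The gap itself survives: no document schedules a pre-operative rating for this primary outcome.

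**Conclusion.** The point holds as a cheap improvement. Without a pre-operative pain rating, comparability on that scale cannot be shown, and neither change from baseline nor ANCOVA on baseline pain is possible. The ANCOVA covariate is also ambiguous. The planned analysis remains feasible and is not biased by the omission.

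The size is modest: relative to no adjustment, the half-width narrows by 0.04 points at r = .3 and 0.13 at r = .5, and the gain over WOMAC adjustment would be smaller. Power for a 1-point difference rises from 52% to 55% or 64%. These figures rest on the plan's SD, 50 analysed patients per arm and assumed correlations. The varying and partly unstated recall period is a secondary matter of definition.

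**What to change.** 1. Add the pain rating to the time-of-consent visit and tick it in the Study Timeline. Use the same instrument as after surgery and name it consistently, since the documents refer variously to a visual analog scale, a numerical score and a 10-point scale.
2. Pre-specify ANCOVA of post-operative pain on baseline pain for every patient, whatever any baseline significance test shows. The precision comes from the correlation with the outcome, not from an observed imbalance. State the covariate explicitly.
3. For patients already enrolled, use baseline WOMAC pain as the covariate. State how the two covariates enter one model, for example with an indicator for which was recorded and a separate slope for each.
4. Give the rating one stated look-back period for all clinic visits, and confine it to the post-operative period on day 1.

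The cost is one question at an existing 35-minute visit, a tick in the timeline and some wording. The downside is a proxy covariate for patients enrolled before the change.

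### Three unranked primary outcomes have no named visit, circumference site, range-of-motion direction, success rule, test order or alpha control

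*Combined protocol and SAP*

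**What the plan says.** In the combined protocol and SAP, the Data Analysis Plan puts three outcomes on an equal footing: "The primary outcomes of range of motion, leg circumference, and pain ratings will be compared post-op between conditions using two-tailed independent t-tests". It then adds: "These comparisons will additionally be made at multiple additional time-points", over a 12-week period.

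On sample size the same section says: "A priori power analyses were calculated for two-tailed independent t-tests for each primary outcome, using an alpha of .05", with power .80, and that "the average of these numbers is used to calculate the final sample size". For pain it assumes "a 2-point change with a standard deviation of 2.5 using a 10-point scale; 84 patients were estimated". For range of motion it gives "10 degrees of difference from a 0-140 degree estimated range of values", and for circumference a 1 cm difference. An effect size of .55 is linked to 106 patients.

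On timing, Study Procedures says: "Patients will be seen back at regularly scheduled post-operative visits of 2 weeks, 4 weeks, 6 weeks and 12 weeks". There is also an evaluation on post-operative day 1. Before these, the leg is measured after wound closure and dressing, and only then is the randomized sleeve or stocking applied. Sleeves are worn as tolerated after 2 weeks and stopped at 6 weeks. In the Study Timeline table, the pain row has no entry in the Post-op column.

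On variables, the list of data to be collected includes "Mid-thigh, mid-knee, and mid-calf measurements in extension", and range of motion in both flexion and extension. No site or direction is marked as primary.

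**The concern.** A primary analysis should be executable by two analysts with the same result. Here one could test mid-calf circumference on day 1 and another mid-knee circumference at week 6, and both would be following the plan. One could declare success on a single outcome and the other could require all three.

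The planned sample size assumes a 5% error rate for each outcome. Without a success rule, nothing ties that 5% to the trial's overall conclusion. An ineffective garment could be reported as better because one of several comparisons crossed .05. The visits are not interchangeable either, since week 12 comes after the garment has been stopped.

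**Working it through.** **1. Does any outcome lead?** The stated sizes are 84 for pain and 106 for d = .55. (84 + 106)/2 = 95, but (84 + 106 + 106)/3 = 98.7, which rounds to the stated 99. So all three outcomes entered the average equally, and the sample size singles none out.

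**2. Which visit is 'post-op'?**

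| Candidate | Garment status | Pain score scheduled? |
|---|---|---|
| Post-op column | measured before garment is applied | no |
| Day 1, week 2 | garment period | yes |
| Weeks 4 and 6 | garment worn as tolerated, stopped at 6 weeks | yes |
| Week 12 | garment stopped | yes |

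The first row cannot serve: one primary outcome would have no data and the other two could not show a garment effect. Five visits remain and none is named.

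**3. False-positive chance if any one result counts, one visit.** For independent tests in either direction it is 1 − (1 − .05)³ = 1 − .8574 = .143. Favouring the garment only, it is 1 − (1 − .025)³ = .073. The documents give no correlations, so I assumed a range and simulated three correlated normal test statistics under no effect, counting |z| > 1.96 (or z > 1.96 for one direction).

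| Outcome correlation | Either direction | Favouring garment |
|---|---|---|
| 0 | .143 | .073 |
| .3 | .136 | .068 |
| .5 | .125 | .063 |
| .7 | .109 | .055 |
| .8 | .098 | .049 |
| .9 | .083 | .042 |

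If any of the three circumference sites may count (three sites, one motion measure and pain; assumed correlation .8 between sites and .3 otherwise), the either-direction figure is .177.

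**4. Power under each rule.** This uses the two-sample t-test (noncentral t) with 50 analysed per arm and no losses.

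- Check on the plan's own figures: d = .55 at .05 and power .80 needs 105.7, so 106, as stated. Pain at 2/2.5 = .80 needs 51.0, so 52, not 84.
- d = .55 tested at .05: 78%. At 45 per arm it is 73%.
- d = .55 at the strictest Holm step, .05/3 = .0167: 62%.
- Pain at d = .80, tested at .05: 98%.
- All three significant with d = .80, .55 and .55 (normal approximation): about 60% at correlation 0, rising to 69% at .7. This is the same event as passing the third step of a fixed order.

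**The case against.** The best defence is that the plan has one lead comparison with later visits in support, because the further time-points are called additional. That reading is fair. It rules out treating every visit as a separate route to a claim, but it does not say which visit leads. A reader might multiply outcomes, sites, directions and visits and quote a much larger error rate. The document does not support that as a headline, because it nowhere says that each visit can support a claim. It does not exclude it either.

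Second, Objectives speaks of the garment proving more effective in these outcome areas, which could mean that all must succeed. That would remove the inflation across outcomes. But it is not a decision rule, and the areas it lists include narcotic use, which is not among the three primary outcomes. It would also leave the choice of site, direction and visit open.

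Third, there are hints about the variables. The device is described as meant to improve swelling in the knee, which points towards the mid-knee site, and a 0-140 degree range suggests flexion or total arc. Neither hint names a variable.

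Fourth, the .05 is stated for the power analyses, and no separate test level is given for the analysis. Testing each outcome at .05 is the natural reading, not an explicit rule.

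Last, a reader might infer that the error rate is always at least doubled. It is not: above an outcome correlation of about .78, the either-direction figure falls below 10%.

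**Conclusion.** The concern holds. The primary test cannot be carried out uniquely from the text, and the only measurement bearing the label Post-op is unusable for it.

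The size is conditional on one significant outcome being enough: 11-14% in either direction at one visit for outcome correlations of .7 to 0, or 8-10% at .9 to .8. This compares with 5% per test. The matching figures in favour of the garment are 5-7% for correlations of .7 to 0, against 2.5%. Freedom over the circumference site alone takes the either-direction figure to about 18%. It would go higher only if several visits could each support a claim. If all three outcomes must succeed, there is no inflation across outcomes, but the free choice of site, direction and visit remains.

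The stated 84 patients for pain should not be read as implying an effect of d of about .62. That effect at power .80 gives 84, but so does the stated d = .80 at power .95 (83.2, rounded up to an even number). The document does not say which was meant, and this is a separate item to reconcile.

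**What to change.** Before outcome data are seen, amend the Data Analysis Plan to:

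- Name one variable per primary outcome and one common visit after garment placement, for example mid-knee circumference, knee flexion and average pain score at 2 weeks. The choice is the sponsor's.
- State one rule: a fixed order with each test at two-sided .05, stopping at the first non-significant result; or Holm; or all three required.
- Label all other sites, directions and visits secondary, reported with confidence intervals and no claim.
- State that the Post-op measurement precedes the garment and is not an outcome.
- Reconcile the 84 for pain with its stated inputs, then restate power for the chosen rule, with an allowance for losses.

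The cost is wording and a lower power statement, not more patients. A d = .55 outcome keeps 78% only if it is tested first, and Holm takes it to 62% at the strictest step. Requiring all three leaves about 60-69%. Holding 80% at the strictest Holm step would take 142 patients (141.3 rounded up to an even number). That is a design change and is not required by this point.
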